#### 7.4.5. Adverse Event Reporting

**Figure 2: Adverse Event Reporting**

\* This post-trial monitoring can be conducted by contacting the patient or the general practitioner, the referral site (if applicable), or by checking medical records or other sources.

Any related SAE that the investigator becomes aware of after end of trial must be reported to sponsor using the clinical AE report form, see [Section 7.4.5.3](#).

#### Non-serious Events:

Non-serious AEs should be reported from the day of first IMP administration until 5 weeks after the patient's last dose. Thereafter and during the follow-up and post-trial monitoring periods, new onset of cancers regardless of causality, should be reported, until death or at least 10 years after end of trial, whichever comes first. During the follow-up period, Grade 3 or higher non-serious AEs considered related to IMP or related to the presence of the indwelling catheter system should be reported. Non-serious AEs occurring between signing the ICF and the first IMP administration must be recorded as medical history.

#### Serious Adverse Events:

Serious AEs should be reported from signing the ICF until 5 weeks after the patient's last dose. Thereafter and during both the follow-up and post-trial monitoring periods, only SAEs considered related to IMP or related to the presence of the indwelling catheter system, or new onset of cancers regardless of causality, should be reported, until death or at least 10 years after end of trial, whichever comes first.

All events meeting the definition of an AE must be collected and reported in the eCRF. SAEs, DLTs (Part 1), and AESIs (whether serious or non-serious) should be reported both in the eCRF and on the clinical AE report form.

During each contact with the trial site staff, the patient must be asked about AEs, for example by asking: "Have you experienced any problems since the last contact?" All AEs observed by the

investigator or patient must be reported by the investigator and evaluated unless specifically excluded. All SAEs and AEs leading to discontinuation of IMP either observed by the investigator or patient must be reported by the investigator and evaluated.

## Diagnosis

The investigator should report the diagnosis, if available. If no diagnosis is available, the investigator should record each sign and symptom as individual AEs using separate AE forms.

## Onset Date and Time

Start date for an (S)AE is the date of occurrence of the first symptom. The time should be entered if the event starts on a dosing day or if the duration of the event is less than 24 hours.

## End Date and Time

The end date should be entered if the outcome of an event is fatal, recovered/resolved, or recovered/resolved with sequelae. The time should be entered if the event starts on a dosing day or if the duration of the event is less than 24 hours.

## Severity

The investigator will use NCI CTCAE Version 5.0 to describe the severity of the AE. The grade assigned by the investigator should indicate the grade at the onset of the event and the most severe grade that occurred during the AE period.

## Outcome

The investigator must judge outcome of the AE by the following terms:

- Recovered
- Recovered with sequelae
  - Description of the sequelae should be provided
- Not recovered
- Recovering
- Fatal
- Unknown\*

\* Should only be used if patient is lost to follow-up.

Instructions for reporting changes in an ongoing AE during a patient's participation in the trial will be provided in the instructions that accompany the AE form in the eCRF.

## Relationship to Investigational Medicinal Product

The investigator must assess whether the event is related to the IMP. A suspected adverse drug reaction (ADR) is defined as one in which there is a reasonable possibility that the drug caused the AE. Relatedness must be assessed and reported from the first time the AE is being reported. When assessing the causal relationship of an AE to the IMP, the following should be taken into consideration:

### Not Related (Unlikely)

The AE is not related to the IMP, which means the AE:

- Does not follow a reasonable temporal sequence from IMP administration.
- Is readily explained by the patient's clinical state or by other modes of therapy administered to the patient.
- Is clearly not related to the IMP.

For AEs assessed as "Not Related", an alternative etiology should be stated detailing the more likely reason for the AE.

### Possibly Related

The AE follows a reasonable temporal sequence from IMP administration but could have been produced by the patient's clinical state, medical history, or the trial procedures/conditions.

Alternative etiology should be provided for all AEs assessed as possibly related to IMP.

### Probably Related

The AE is probably related to the IMP, which means the AE:

- Follows a reasonable temporal sequence from IMP administration.
- Abates spontaneously upon discontinuation of the IMP (de-challenge) without any curative treatment.
- Is confirmed by reappearance of the same reaction on repeat exposure (re-challenge) (if applicable).
- Cannot be reasonably explained by the known characteristics of the patient's clinical state or medical history.

## Action Taken with Investigational Medicinal Product

The action taken with the IMP should be noted as:

- Dose Decreased\*
- Dose Administration Rate Decreased
- Interrupted
- Postponed
- Discontinued
- None
- Not Applicable\*\*
- Unknown.

\*Only applicable in Part 2.

\*\*Not Applicable should be used if the AE occurs before first treatment or after end of treatment (i.e., the IMP was already discontinued).

### **7.4.5.1. *Events Requiring Immediate Reporting***

The following events (for reporting periods, see [Figure 2](#)) require immediate reporting (within 24 hours) (for details, see [Section 7.4.5.3](#)):

- SAE
- DLT
- AESI
- Pregnancy.

Starting five weeks after the last dose, only SAEs or Grade 3 or higher AEs at least possibly related to Lu-DTPA-omburtamab or to the presence of the indwelling catheter system, or new onset of cancers regardless of causality, should be reported until end of trial. Subsequently, in the post-trial monitoring period, SAEs considered related to IMP or new onset of cancers regardless of causality, should be reported until death or at least 10 years after end of the trial, whichever comes first, using the clinical AE report form, see Section [7.4.5.3](#).

#### **7.4.5.2. *Pregnancy***

Any pregnancy that occurs during trial participation must be reported to the sponsor within 24 hours of knowledge using the pregnancy form. Pregnant trial patients must be discontinued from treatment immediately. Should pregnancy of female partners of male patients occur, a separate informed consent will be obtained from the female partner for collection of information regarding the pregnancy. The pregnancy must be followed up to determine outcome and status of mother and child. The child must be followed at least to the age of 1 month. Pregnancy complications and elective terminations for medical reasons must be reported as an AE or SAE. Spontaneous abortions must be reported as an SAE.

#### **7.4.5.3. *Reporting Timelines and Contact Details***

- Initial SAEs (including DLTs and predefined AESIs, whether serious or not): The clinical AE report form must be reported from site to sponsor within 24 hours of the investigator's first knowledge of the event. The clinical AE report form is to be e-mailed as detailed below. The AE eCRF page should be updated in accordance with agreed data entry timelines and the eCRF completion instructions. New follow-up information available at site must be reported within 24 hours.
- Follow-up information requested from the sponsor must be replied to within 3 working days using a data clarification form. The AE eCRF page should be updated in accordance with agreed data entry timelines.
- If an ongoing SAE/AESI changes in intensity, relationship to IMP, or as new information becomes available for the event, a clinical AE report form should be completed and sent to the sponsor within 24 hours of the change in assessment.

#### **7.4.5.4. *Reporting of SUSARs***

All relevant information about Suspected Unexpected Serious Adverse Reactions (SUSARs) will be reported to regulatory authorities in accordance with regulatory requirements.

Investigators will be notified of SUSARs in accordance with local requirements. Furthermore, investigators will be informed of any trial-related SAEs that may warrant a change in any trial

procedure. Labcorp will inform the IRBs/ECs of SUSARs in accordance with local requirements, unless locally this is an obligation of the investigator. The Sponsor assessment of expectedness for Lu-DTPA-omburtamab will be performed according to the current version of the investigator's brochure.

#### **7.4.5.5. *Follow-up on Adverse Events***

Non-serious AEs should be followed until they are either resolved, returned to baseline, or until end of trial, whichever comes first. Grade 3 or higher non-serious AEs that are considered treatment related and all SAEs (including AESIs and DLTs) should be followed on a regular basis, according to the investigator's clinical judgment, until the event has been resolved or until the investigator can assess it as chronic or stable. This includes follow-up during the long-term monitoring periods.

#### **7.4.5.6. *Medical Monitoring and Communication of Significant Safety Issues***

In the event of any significant safety related issues, the investigator should:

- Closely monitor the patient
- Contact the Medical Monitor (for contact details, see the protocol front page)

Sponsor will decide upon immediate action to be taken including prompt notification of the DMC and will communicate to regulatory authorities, investigators, ECs/IRB, and patients as needed within regulatory timelines.

The Sponsor will ensure that all Investigators across sites and ongoing trials with the same IMP (Lu-DTPA-omburtamab) are promptly notified of significant safety issues and required actions including urgent safety measures (e.g., holding further dosing) to protect trial participants against an immediate hazard.

In addition, the Sponsor will inform all Investigators across sites and ongoing trials with the same IMP (Lu-DTPA-omburtamab) of DMC recommendations including dose escalation decisions.

## 8. SAMPLE SIZE AND DATA ANALYSES

### 8.1. Determination of Sample Size

In Part 1, the chosen sample size is customary for studies of this nature and is not based on statistical considerations. It is estimated that up to 25 patients will participate in Part 1, based on 5 dose levels being recruited. Actual number of patients will depend on the number of DLTs observed.

For Part 2, a sample size of 24 patients provides at least 90% probability to detect an AE occurring in 10% of exposed patients.

The assumption is that 20 out of the 24 patients in Part 2 are evaluable. With 20 patients evaluable for response and a response rate of 25% (~ to 5 responders out of 20), the lower limit of the 95% confidence interval will be 9%.

### 8.2. Analysis Populations

The following analysis sets will be included for this trial:

**Safety Analysis Set:** will consist of all patients who received at least 1 dose of trial treatment (treatment dose or dosimetry dose).

**DLT Evaluable Analysis Set:** will include patients in the dose escalation who as a minimum is evaluated during the 5 weeks DLT evaluation period, or who has a DLT during the DLT evaluation period. This analysis set is a subset of the Safety Analysis Set.

**Full Analysis Set (FAS):** will consist of all patients in the Safety Analysis Set.

**Dosimetry Analysis Set (Part 1 only):** will consist of all patients who received the dosimetry dose and have evaluable data for absorbed doses to CSF and blood or for whole-body planar scan.

**PK Analysis Set:** will consist of all patients who received at least 1 treatment dose of trial drug and have evaluable PK data.

Efficacy will be analyzed using the FAS. Safety will be analyzed using the Safety Analysis Set. Dosimetry and absorbed doses to CSF and blood will be analyzed using the Dosimetry Analysis Set. Pharmacokinetics will be analyzed using the PK Analysis Set.

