### ***3.1.1.1. Dose Escalation and Stopping Rules***

As detailed in [Section 4.4](#), a DMC will be formed to independently review the safety data from previous dose level(s) and make recommendations on whether dose escalation should continue. Based on the DMC recommendation, following review by the sponsor, the doses may be escalated or reduced and may be lower than the starting dose.

The starting treatment dose of lutetium-177 in Part 1 will be 10 mCi. Planned dose escalations (with a 3+3 design) are 25, 50, 65, and 85 mCi. Up to 1 additional dose level may be recruited to investigate an intermediate dose of investigational medicinal product (IMP), if warranted based on the safety findings from previous dose level(s). The requirement for an additional dose level will be agreed with the sponsor in consultation with the DMC and will be documented in the

Trial Master File. Dosing at any additional dose level will be subject to the same dose-escalation rules as for the planned dose levels, as described below. The maximum planned dose is 85 mCi.

Initially, 1 patient will be allocated to Dose Level 1 and subsequent dose escalations will be conducted using a classic 3+3 design. If no treatment-related Grade 3 or higher AEs are observed in the first patient, escalation from Dose Level 1 to Dose Level 2 will proceed with 3 patients being allocated to Dose Level 2, after DMC evaluation and recommendation. If a Grade 3 or higher treatment-related AE occurs, a further 2 patients will be enrolled at Dose Level 1.

The DMC will receive all SAE on an ongoing basis. The DMC will make the final assessment of whether the event qualifies as a DLT.

The first enrolled patient in each dose level will be observed for a minimum of two weeks after the treatment dose before subsequent patients will be dosed at the same dose. During the two weeks of observation, safety surveillance will focus on DLTs (including myelosuppression). If a DLT is observed in the first patient, a second patient will be included and observed for a minimum of two weeks after the treatment dose before the third patient is included. If no DLT is observed in the first patient, two subsequent patients will receive the treatment dose, but at least two days apart.

Escalation and de-escalation decisions will then be determined by the number of DLTs (as defined in [Section 3.1.1.2](#)) observed during Cycle 1 and the number of patients evaluable for DLTs, as follows.

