### ***3.1.1.2. Definition of Dose-limiting Toxicity***

DLTs are defined as AEs (graded according to CTCAE version 5) occurring within 5 weeks after first IMP administration in Cycle 1 of Part 1 and that are considered possibly or probably related to IMP and meet any of the following criteria:

- Grade 4 myelosuppression (i.e., anemia, thrombocytopenia, or neutropenia) lasting more than 1 week, or more than 3 weeks following intervention (e.g., blood transfusion or granulocyte-macrophage colony-stimulating factor [GM-CSF])
- Any other Grade 4 hematological AE
- Grade  $\geq 3$  thrombocytopenia associated with bleeding
- Grade  $\geq 3$  febrile neutropenia (i.e., fever concurrent with neutropenia) lasting more than 5 days despite use of growth factors and antibiotics
- Grade 4 infusion-related reactions/anaphylaxis
- Grade 3 infusion-related reactions (excluding fever and Grade 3 abnormal laboratory values) that do not resolve to Grade  $\leq 1$  within 5 days of onset.
- Any non-hematological Grade  $\geq 3$  AE that is not listed in the list of exemptions below

DLTs must be entered onto the clinical AE report form and be reported from site to sponsor within 24 hours of the investigator's first knowledge of the event (see [Section 7.4.5.2](#)). If any of the side effects mentioned in the DLT definitions occur during Cycle 2 in Part 1, these will be discussed at the first upcoming preplanned DMC meeting, and the Sponsor Safety Committee will evaluate the DMC recommendations for further dosing.

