## **8.5. Safety Analysis**

### **8.5.1. Dose-Limiting Toxicities**

DLTs observed during the DLT evaluation period, i.e., within 5 weeks after the dosimetry dose in Cycle 1 of the dose escalation will be listed and summarized by Medical Dictionary for Regulatory Activities (MedDRA) system organ class (SOC) and preferred term (PT). DLTs observed outside the DLT evaluation period will be presented in a listing. The information from

the DLTs will be used to guide the escalation and ultimately determine the MTD. Furthermore, the information will be used to make recommendations regarding the RP2D. The evaluation of DLTs will be based on the DLT evaluable analysis set.

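### The DLT Evaluable Set does not require the Cycle 1 treatment dose for a DLT-free patient, and its five-week window stays fixed to the dosimetry dose when the treatment dose is delayed

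*Combined protocol and SAP*

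**What the plan says.** **The set.** Section 8.2 (repeated in the Synopsis) defines a DLT Evaluable Analysis Set that "will include patients in the dose escalation who as a minimum is evaluated during the 5 weeks DLT evaluation period"; a DLT in that period also qualifies a patient. It is a subset of the Safety Analysis Set, for which a dosimetry dose alone is enough. The PK Analysis Set in the same section does carry a treatment condition: it "will consist of all patients who received at least 1 treatment dose of trial drug and have evaluable PK data".

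**The window.** Section 3.1.1.2 defines DLTs as events "occurring within 5 weeks after first IMP administration in Cycle 1 of Part 1". Section 8.5.1 names the same start: "DLTs observed during the DLT evaluation period, i.e., within 5 weeks after the dosimetry dose in Cycle 1 of the dose escalation". It adds that "DLTs observed outside the DLT evaluation period will be presented in a listing".

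**The treatment dose.** It is planned for Day 8 (±1) in Appendix 3, Table 6. Section 3.1 and footnote 1 of Table 6 allow the schedule to be adjusted for individual patients. Neither gives a maximum delay for this dose or extends the DLT window.

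**The use.** Section 3.1.1.1 bases escalation on the DLTs "observed during Cycle 1 and the number of patients evaluable for DLTs", and Section 8.5.1 evaluates DLTs on the DLT Evaluable Set.

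**Replacement.** Section 4.3.4 replaces Part 1 patients who stop between the dosimetry dose and the first treatment dose. It also sends to the DMC the question of replacing a patient who stops because of an IMP-related AE.

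**The concern.** The set should contain patients who give evidence about the tolerability of their assigned level. Two kinds of patient can be counted in full while giving less than that.

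The first received only the 5 mCi dosimetry dose. Sections 3.1.1, 4.3.2.1 and 5.1 stop a patient who has a Grade 3 or 4 non-hematologic AE after that dose, whatever its cause. A DLT, however, must be "considered possibly or probably related to IMP and meet any of the following criteria", and Section 3.1.1.2 exempts some Grade 3 events. A patient can therefore be stopped without a DLT. Section 4.3.2.1 keeps such a patient in follow-up, so five weeks of evaluation can be completed and the definition met.

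The second received the treatment dose late. The window ends on the same day regardless, so the time at risk after the escalated dose shrinks day for day. A DLT-free result from such a patient is weaker evidence, and an event after the window does not enter the formal DLT evaluation.

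**Working it through.** **Plan's own figure.** Section 8.1 gives up to 25 patients over five levels. One patient at Dose Level 1 plus four levels of six gives 1 + 4 × 6 = 25, so the figure is reproduced. Nothing below changes it.

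**Composition of the set.** Add one DLT-free dosimetry-only patient who has been replaced:
- Cohort of 3 with one DLT: 1/3 = 33.3% becomes 1/4 = 25.0%.
- Cohort of 6 with one DLT: 1/6 = 16.7% becomes 1/7 = 14.3%.

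**Post-treatment days in the window.** Five weeks after Day 1 is Day 36, so days observed = 36 − treatment day.

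| Treatment day | Days observed |
|---|---|
| 7 / 8 / 9 (on schedule) | 29 / 28 / 27 |
| 15 (7 days late, illustrative) | 21 |
| 22 (14 days late, illustrative) | 14 |

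**Effect on clearing a level.** A level clears with 0 DLTs in 3 patients, or with 1 in 3 followed by 0 in the next 3. With P0 and P1 the chances of 0 and 1 DLT in the first three, P(clear) = P0 + P1(1−p)³. The documents give no DLT rate, so p = 0.20 and 0.30 are assumed.

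All on time, P0 = (1−p)³ and P1 = 3p(1−p)²:
- p = 0.20: 0.512 + 0.384 × 0.512 = 0.709
- p = 0.30: 0.343 + 0.441 × 0.343 = 0.494

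Now let one of the first three be late. Assume onset uniform over the 28 days after treatment. That patient's observable rate is cp, with c = 21/28 = 0.75 or 14/28 = 0.50. Then P0 = (1−p)²(1−cp) and P1 = 2p(1−p)(1−cp) + (1−p)²cp.
- p = 0.20, 7 days late: 0.544 + 0.368 × 0.512 = 0.732
- p = 0.20, 14 days late: 0.576 + 0.352 × 0.512 = 0.756
- p = 0.30, 7 days late: 0.380 + 0.436 × 0.343 = 0.529
- p = 0.30, 14 days late: 0.417 + 0.431 × 0.343 = 0.564

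**Replacement after a dosimetry-only DLT.** Such a DLT is counted, so the level clears only if all other patients are DLT-free. At p = 0.20:
- Not replaced (two others plus three more): 0.8⁵ = 0.328
- Replaced (three others plus three more): 0.8⁶ = 0.262
- Difference: 0.066

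The chance of exactly one such event among three patients is 3q(1−q)². At an assumed q of 1%, 2% or 5% it is 0.029, 0.058 or 0.135. Times 0.066, this gives about 0.2, 0.4 or 0.9 percentage points per level.

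**Interaction with Cycle 2.** Appendix 3, Table 7, footnote 1 starts Cycle 2 35 days after the dosimetry dose, which is Day 36, adjustable per patient. Holding 28 post-treatment days ends on Day 8 + 28 = Day 36 when on schedule, but on Day 43 or Day 50 after a 7- or 14-day delay. For a late patient the two timings must be reconciled.

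**The case against.** The strongest reply is that the dosimetry-only gap changes no escalation decision. That is largely right. Section 4.3.4 replaces the patient, and Sections 3.1.1.1 and 3.1.2 refer to patients treated at a level when they call for six before naming an MTD. The escalation rules use counts in three and then six patients, not a rate. Section 8.5.1 plans a listing and a summary by organ class and preferred term, and names no DLT proportion per level. A reader might infer that an untreated patient can carry a level through escalation; the documents do not support that. What stands is that nothing removes the replaced patient from the set on which DLTs are evaluated.

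On the window, a reader might infer that Sections 3.1.1.2 and 8.5.1 conflict. They agree, because the first IMP in Cycle 1 is the dosimetry dose. Nor is the rule that the first patient at each level "will be observed for a minimum of two weeks after the treatment dose before subsequent patients will be dosed at the same dose" a competing evaluability window. It staggers dosing and covers only that patient. Late events are not hidden either: the DMC receives SAEs as they occur (Section 3.1.1.1), reviews available safety data after Cycle 1, and discusses DLT-type events from Cycle 2 (Section 4.4). These points limit the harm, but the written rule still counts a short observation as a full one.

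A reader might also infer that a DLT after the dosimetry dose alone goes uncounted. Sections 3.1.1.2, 8.2, 8.5.1 and 3.1.1.1 together already count it. Only replacement is unclear.

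Figure 1 is not reproduced in the text available here, and the DMC Charter is a separate document. Either may add detail.

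**Conclusion.** The point holds in a limited form, between minor and should-fix. As written, the set can include a DLT-free patient who never received the assigned treatment dose. Replacement confines the consequence mainly to the analysis set. The more important gap is that a delayed treatment dose shortens the observation that counts, one day per day of delay, without affecting evaluability.

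For one late patient among the first three, the illustrative rise in the chance of clearing a level is about 2 to 5 percentage points at a 20% DLT rate (71% to 73% or 76%). At 30% it is about 4 to 7 points (49% to 53% or 56%). These figures are conditional on a delay occurring. They rest on assumed DLT rates, assumed delays of 7 and 14 days, and uniform onset over 28 days. The documents do not say how often delays occur, so the unconditional effect is unknown and smaller. The replacement ambiguity is worth less than 1 point per level under the rates assumed.

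**What to change.** 1. In Section 8.2 and the Synopsis, require receipt of the Cycle 1 treatment dose for a DLT-free patient to be evaluable at the assigned level. Keep patients with a DLT in the set as now.
2. In Section 8.2, the Synopsis, and Sections 3.1.1.2 and 8.5.1, state that a DLT-free patient is evaluable only after a post-treatment observation period counted from the actual treatment date. The sponsor sets its length, such that a delayed dose does not reduce it below what the schedule already gives on-time patients. Reconcile this with the Cycle 2 start in Appendix 3, Table 7.
3. Reconcile the two sentences of Section 4.3.4 on whether a patient with a DLT after the dosimetry dose alone is replaced. This review does not choose the rule.

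**Cost:** a protocol amendment with regulatory and IRB/EC approval (Appendix 2). A cohort waits by the length of any treatment delay, and Cycle 2 shifts to match for that patient. No added patients are planned.
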